**Primary and Secondary Outcome Measures:**

The pre-post surveys will assess the following behavioral measures:

1. Primary Testing Outcome: COVID-19 antigen testing using individual-level data.
2. Secondary Vaccination Outcome: COVID-19 vaccination uptake using individual-level data.
3. Secondary Outcomes: Mitigation measures if a positive test is obtained including mask wearing, isolating, and notifying close contacts.

**Study Survey:** Project personnel will use the survey platform REDCap (Research Electronic Data Capture) survey software to collect the study survey responses from the participants who consent. The survey instrumentation is designed to capture all relevant demographic characteristics, personal history regarding COVID-19 infection (self, others), testing and vaccination behavior, and psychosocial determinants for testing and vaccination behavior. This survey is composed of all RADx Common Data Elements (CDEs) required by our funder, survey measures taken or adapted from extant COVID-19 health promotion research for our RADx Phase I 2-1-1 survey.

## Summary of Embedded Study Survey Constructs

Measures / Constructs	Questions	Citation/Tool
Testing behavior	Testing for COVID-19, ever tested, last 30 days, positivity, access to testing	Funder required items, Novel items
COVID-19 history	COVID-19 sickness, hospitalization (self or others)	Funder required items, Novel items
Intention to test	Likelihood of testing (ever, 30 days), intention to test as needed	Funder required items, Novel items
Self-efficacy to test	Certainty of ability to be tested given situational contexts	Adapted self-efficacy measures following Maibach (1995) 
Pandemic safety behaviors	Wearing masks in private settings, wearing masks in public settings, washing/sanitizing hands, intentional social distancing (Never, some of the time, very often, all of the time)	Adapted for CEAL Program from Center for Economic and Social Research Understanding America Study Coronavirus Tracking Survey. https://www.phenxtoolkit.org/covid19/source
Vaccination	Vaccine uptake, type, doses	Funder required items
Trusted Sources of Information	Sources of information (doctor, media, health department, etc)	Funder required items
COVID-19 Perceived Susceptibility/Severity	How concerned are you about contracting COVID-19? How likely is it that you will get COVID-19?	Savoia E. et al, 2021 

## Study Procedures

### Sample Selection via Convenience Sampling- Houston/Harris County and Cameron County

Study personnel from the Houston/Harris County & Cameron County areas will prepare for each PBG randomized to the study by mapping all streets in the selected PBG using Google Maps. Study personnel (CHWs) will approach each house as they recruit through the PBG, skipping those homes where current or past Phase II embedded study participants live. The CHWs will work in teams. One member of the team will work one side of the street and the other will work the other side of the street, both following the same sampling protocol. There may be occasions when it is appropriate that both team members work the same side of the street approaching the same houses together. Each attempt, successful or unsuccessful, will be recorded on a tracking sheet with items such as date and time attempted, address, identifying characteristics of households approached, whether individuals fit the inclusion and exclusion

study criteria, whether individuals consented to the study, reason for refusal or no answer, whether the survey was completed, whether Wi-Fi was available and barriers to visiting completion.

In addition, study personnel from the Houston/Harris County & Cameron County areas will identify community organizations where recruitment may be conducted, as informed by the social network data. In collaboration with selected organizations, study personnel will screen organization/event attendees by introducing themselves and the study, verifying eligibility, and scheduling an appointment at the individual's home where the remainder of the baseline visit may take place (unless the participant prefers to complete the entire baseline visit at that time). Staff will primarily recruit community members at these community events, but recruitment strategies may include posting recruitment fliers/posters at collaborating clinics, organizations, and businesses. Interested individuals will then call the contact listed on the poster to get more information about the study and learn how to participate. Study personnel can then screen the individual over the phone and if eligible, can schedule an appointment at the individual's home, where the remainder of the baseline visit will take place. Each community-based recruitment attempt, successful or unsuccessful, will be recorded on a tracking sheet with items such as date and time attempted, address of the collaborating organization, whether individuals fit the inclusion and exclusion study criteria, whether individuals consented to the study, reason for refusal, whether the survey was completed, whether Wi-Fi was available and barriers to visiting completion.

### **Sample Selection via Convenience Sampling- Northeast Texas Region**

Study personnel from the Northeast Texas region will approach each PBG randomized to the study by mapping out all streets in the selected PBG using Google Maps. On each PBG map, they will identify community organizations where recruitment may be conducted with priority to those shown as salient in the social network analysis. In collaboration with selected organizations, study personnel will screen organization/event attendees by introducing themselves and the study, verifying eligibility, and scheduling an appointment at the individual's home where the remainder of the baseline visit may take place (unless the participant prefers to complete the entire baseline visit at that time). Staff will primarily recruit community members at these community events, but recruitment strategies may include posting recruitment fliers/posters at collaborating clinics, organizations, and businesses. Interested individuals will then call the contact listed on the poster to get more information about the study and learn how to participate. Study personnel can then screen the individual over the phone and if eligible, can schedule an appointment at the individual's home, where the remainder of the baseline visit will take place. Each community-based recruitment attempt, successful or unsuccessful, will be recorded on a tracking sheet as described in the previous paragraph.

### **Consent**

CHWs will approach each house or organization/event identified using the sample selection procedure described above with scripted information describing the research study, eligibility criteria, the Phase III main study survey, a COVID-19 resource flier, and the incentive for participating. If the resident is interested, the eligibility of individuals in the household will be determined using a brief screening based on the inclusion criteria described above. Participation will be limited to one person per household. If more than one individual in the home is interested and is eligible to participate, the person with the nearest birth date to the date of enrollment will be enrolled. Upon confirming eligibility and which household member will be enrolled, CHW will review the informed consent form on paper copy or

electronically and acquire the individual's signature confirming consent. The individual will receive a paper copy of the consent or receive it electronically for their records.

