**Study Population:**

In the intervention study arm, we will enroll up to 431 individuals and 400 historical control group participants.

**Inclusion/exclusion criteria for intervention study arm.** In this study, the inclusion criteria for the enrolled intervention study arm individuals include being aged 18 years to 89 years and having a smartphone that accepts text messages. The exclusion criteria will include: (1) having been diagnosed with COVID-19 in the past 30 days based on a positive test (antigen or PCR) or a clinical diagnosis, (2) having tested for COVID-19 with PCR or antigen test within the past 30 days, (3) not being available in the recruitment area in the next 60 days, (4) having been an embedded study participant and (5) having been a snowball study participant.

**Selection of the study population.** Three large regions of Texas: 1) Houston/Harris County; 2) Cameron County in South Texas; and 3) seven counties, including the city of Tyler in Northeast Texas. The communities prioritized in this proposal include populations with medical comorbidities, and underserved Hispanics and African Americans in three racially diverse regions: South Texas, Houston/Harris County, and Northeast Texas.

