Upon completion of the baseline survey part A, the participant will receive the first incentive card valued at \$50. Study personnel will also make an appointment for the 8 weeks follow-up post-survey to be conducted by phone (or in person, depending on participant preference) and obtain contact information to follow up throughout the 8 weeks period with intervention related messages or answer participant questions. The staff will send a reminder of the 8 weeks follow-up appointment to the participant. The time frame for the follow-up appointment will be determined by study personnel counting out 8 weeks from the initial home visit. However, because the participant's schedule and availability will be accounted for, the earliest this follow-up appointment can be completed will be 5 weeks from the initial visit and as late as the last day of data collection for that PBG, which could be approximately 4 months from the initial visit. The week and day prior to the post-survey appointment, study personnel will send reminders. The phone-based post-survey will take up to 30 minutes, and the participant will be issued a second incentive card valued at \$35 for their participation in the post survey, which will be mailed or emailed to the participant by study personnel if the follow-up was done via phone. If the participant prefers, the follow-up appointment can be completed in person instead of over the phone, and the incentive will be given in person as well.

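### Telling residents the eligibility criteria and the incentive before screening creates a risk that recent testers deny testing, enrol, and later count as pre-post gains

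*Combined protocol and SAP*

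**What the plan says.** **Order of events.** Under Consent, the opening contact consists of "scripted information describing the research study, eligibility criteria, the Phase III main study survey, a COVID-19 resource flier, and the incentive for participating". The next step is: "If the resident is interested, the eligibility of individuals in the household will be determined using a brief screening". The consent form is reviewed only after eligibility is confirmed, so the early disclosure of criteria is not the consent step. For community organizations and events, the Houston/Harris and Cameron text says "study personnel will screen organization/event attendees by introducing themselves and the study, verifying eligibility", and the Northeast Texas text follows the same sequence. People who respond to a poster are screened by phone.

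**The criterion.** The exclusions under Study Population include "having tested for COVID-19 with PCR or antigen test within the past 30 days". No record check or other verification of testing history is described.

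**Payment.** Under Recruitment: "Upon completion of the baseline survey part A, the participant will receive the first incentive card valued at" $50. The follow-up card is $35, paid for taking part in the post-survey. Nothing ties it to the testing answer.

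**The endpoint.** The primary outcome is "COVID-19 antigen testing using individual-level data", with no look-back period. The survey construct table lists "Testing for COVID-19, ever tested, last 30 days, positivity, access to testing". Neither the outcome section nor the sample size section says which item is used. The primary hypothesis is a rise from baseline to follow-up within the intervention cohort, tested by McNemar's test with a pre-post odds ratio.

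**The concern.** The screening question concerns the same behavior as the primary outcome. At baseline, admitting a recent test costs the respondent enrolment and the $50 card. At follow-up, admitting a test costs nothing. If the criteria are stated first, the respondent may know the qualifying answer before the question is put.

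A recent tester who denies the test should have been excluded but enters the cohort. If that person repeats the denial in the baseline survey and tests again before follow-up, the pair is scored no/yes, a gain in the intervention's favor. The same responses feed the pre-post odds ratio and the GLMM with time as a fixed effect. Adjusting for baseline testing in that model would use the misreported answer. The error can only favor the intervention.

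**Working it through.** **1. The plan's own figure.** Inputs from the sample size section: discordance 0.19, OR 2.5, one-sided alpha 0.025, power 80%, 45% loss to follow-up.

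- Gains: 0.19 × 2.5/3.5 = 13.6%. Losses: 0.19/3.5 = 5.4%. Net: 8.1%, which the plan rounds to 8%.
- The exact conditional McNemar test, averaged over a Binomial(n, 0.19) number of discordant pairs, first reaches 80% power at n = 237 (power 0.8001). This matches the plan.
- Enrolment: 237/(1 − 0.45) = 431, which also matches.
- In people, the planned net effect is 237 × 0.0814 ≈ 19 pairs.

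**2. What the baseline item implies.** If the endpoint uses the 30-day item, every correctly and honestly screened participant is essentially a baseline no, and the loss cell is essentially empty. The sizing has 5.4% in that cell. So either the endpoint uses another window, or the preliminary data behind the sizing did not carry this exclusion.

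**3. Size of the risk under a 30-day item.** None of the rates below is in the documents; all are assumptions. Let

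- π = share of people approached who tested in the past 30 days (10% or 20%)
- c = share of those who conceal it (10% to 50%)
- a = chance that a recent tester reports testing again at follow-up (30% or 50%)
- b = the same chance for someone who had not tested recently

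Suppose there is no intervention effect, the background rate is stable, the follow-up window has the same length, and concealers complete follow-up as often as others. Then:

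- πa + (1 − π)b = π, so b = π(1 − a)/(1 − π)
- share of concealers among those enrolled: w = πc/(πc + 1 − π)
- false gains from concealers: w × a
- recorded rise from the exclusion alone (c = 0): b
- addition due to concealment: w(a − b)

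| π | a | Exclusion alone, b | False gains w·a, c = 10% | False gains w·a, c = 50% | Addition w(a − b), c = 10% to 50% |
|---|---|---|---|---|---|
| 10% | 30% | 7.8 points | 0.3% | 1.6% | 0.2 to 1.2 points |
| 10% | 50% | 5.6 points | 0.5% | 2.6% | 0.5 to 2.3 points |
| 20% | 30% | 17.5 points | 0.7% | 3.3% | 0.3 to 1.4 points |
| 20% | 50% | 12.5 points | 1.2% | 5.6% | 0.9 to 4.2 points |

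Lowest corner: w = 0.01/0.91 = 0.011, and 0.011 × 0.30 = 0.3%. Highest corner: w = 0.10/0.90 = 0.111, and 0.111 × 0.50 = 5.6%. Among 237 completers that is about 1 to 13 people, against the planned net of about 19 pairs.

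False gains exceed the net addition because each concealer displaces part of a cohort that would itself show some testing at follow-up. In every row the exclusion alone contributes more than concealment does.

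**4. Longer windows.** If the item is ever tested, or covers a period well beyond 30 days, a person who denied a test in the past 30 days may truthfully answer yes on the strength of an earlier test. Bias then needs a second false answer that the screener does not force.

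**The case against.** The strongest reply is that the mechanism is partly inferred, and much of this stands.

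- The script is not shown, so it is not certain that it recites the 30-day criterion.
- The documents do not place the testing item in Part A. Part B is completed electronically at the participant's convenience.
- Screening and survey need not share a visit. Event and phone recruits may be seen later at home, and Part A may be deferred by up to 7 days or done virtually.
- The $50 follows completion of Part A. Nothing says that an inconsistent later answer forfeits it.

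These points make the likely size smaller. They do not remove the incentive at screening.

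A reader might infer that the order of the script biases the baseline under any look-back that includes the past 30 days. The documents do not support that, for the reason in step 4 of the working.

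A reader might also turn the false gains into false-positive rates for the McNemar test, keeping the plan's loss cell of 5.4%. That calculation does not measure what the script adds. Under a 30-day item the loss cell is essentially empty, and six gains with no losses already reach significance (0.5^6 = 0.0156; 0.5^5 = 0.031 does not). With 5.4% testing at follow-up, no losses and no concealment at all, the exact test at n = 237 rejects about 99% of the time. Under longer windows, where losses are possible, the forced false answer disappears.

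Finally, the plan also compares the cohort with historical controls, through a ratio of odds ratios and a GLMM. If the Phase II controls were screened in the same way, some of the bias would offset. Their screening is not described, so neither the offset nor its absence is shown.

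**Conclusion.** The concern holds as a risk. The order of disclosure, the exclusion, the payment and the lack of described verification are all in the text, and together they push in one direction at baseline only. A reader might go further and conclude that the baseline answer is in fact biased and the rise inflated. The documents do not show this, since they give neither a misreporting rate nor the script wording.

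The risk matters mainly if the endpoint uses the 30-day item. Under the assumed rates, false gains are about 0.3% to 5.6% of participants against a planned net effect of 8%. Only the most extreme corner (20% recent testers, half concealing, half testing again) exceeds 5%. The net addition to the recorded rise is 0.2 to 4.2 points, secondary to the 5.6 to 17.5 points that the exclusion alone can produce in the same scenarios. Correcting the script would not remove that larger artifact.

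**What to change.** - In the Consent section, take the detailed eligibility criteria, at least the one on recent testing, out of the opening script. Introduce the study in general terms and run the screener first.
- Ask neutrally for the date of the last COVID-19 test, placed among other items, so that the qualifying answer is not evident.
- Use the same order at organizations and events and in phone screening, in all three regions.
- Check that the recruitment posters, which are attached but not shown, do not state this criterion.

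Full information is still given at the consent review before signature.

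**Cost.** A script and screener edit with an IRB amendment, and a few more people screened who prove ineligible. The version is dated 11/07/2024 and the study runs from July 2024 to February 2025, so enrolment may be under way. In that case the change reaches only later enrollees. Its date should be recorded so that results can be shown before and after it.

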## Recruitment

The participant's consent will be documented in REDCap survey software that was developed with a field to capture the participant's consent in participating in the study and the date that informed consent was confirmed. Once the participant's consent is confirmed, study personnel will administer the baseline Phase III main study survey. The baseline survey includes part A, which is completed at the actual time of enrollment. Part B of the survey will also be sent to the participant electronically so that they can complete those items at their convenience. The study staff will record the responses to part A of the survey for the participants into the REDCap platform on a The University of Texas Health Science Center at Houston (UTHealth) secured device. After part A of the survey is completed, study personnel will provide participants with a COVID-19 resource flier. If the participant does not have time to complete the baseline survey part A at the initial home visit, study personnel will make an appointment to either return within 7 days or offer to complete the survey option virtually. The entire visit (introduction, screening, and survey) may take up to 1 hour.

Upon completion of the baseline survey part A, the participant will receive the first incentive card valued at \$50. Study personnel will also make an appointment for the 8 weeks follow-up post-survey to be conducted by phone (or in person, depending on participant preference) and obtain contact information to follow up throughout the 8 weeks period with intervention related messages or answer participant questions. The staff will send a reminder of the 8 weeks follow-up appointment to the participant. The time frame for the follow-up appointment will be determined by study personnel counting out 8 weeks from the initial home visit. However, because the participant's schedule and availability will be accounted for, the earliest this follow-up appointment can be completed will be 5 weeks from the initial visit and as late as the last day of data collection for that PBG, which could be approximately 4 months from the initial visit. The week and day prior to the post-survey appointment, study personnel will send reminders. The phone-based post-survey will take up to 30 minutes, and the participant will be issued a second incentive card valued at \$35 for their participation in the post survey, which will be mailed or emailed to the participant by study personnel if the follow-up was done via phone. If the participant prefers, the follow-up appointment can be completed in person instead of over the phone, and the incentive will be given in person as well.

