## Project Materials

### Intervention Arms:

**Multilevel Community Just-In-Time Network informed Adaptive Intervention (MC-NET-JITAI):** As previously described, recruitment of participants to the MC-NET-JITAI will take place at the participant's home or at one of the salient community organizations that our participants look to and interact with around COVID-19 topics identified through the social network data. CHWs will consent and enroll participants in the MC-NET-JITAI from the randomized PBGs. MC-NET-JITAI will include Community Health Workers (CHW) providing the participant with a batch of 4 rapid antigen tests that can be shared with people in the household or other close contacts if needed, a COVID-19 resource flier tailored to the study region and updated information about COVID-19 testing and vaccination. The intervention will consist of enhanced behavioral and educational text messages, up to three messages each week, providing updates on COVID-19 testing and vaccination. The text messages will include digitally-delivered intervention content such as a video with low-literacy instructions for administering the rapid antigen tests, guidance if they tested positive (e.g., quarantine, notify contacts, wearing a mask), and other relevant strategies and content focused on increasing COVID-19 testing and vaccination. The CHWs will also be available by phone to the participants for any follow-up questions. CHW will follow up via text, email and/or phone with the participants during the two months post-enrollment. In addition to the intervention, the participants will be asked to complete the pre and post-test surveys. Post surveys will be administered online, over the phone, or in person two months after the initial intervention.

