### Sample Size for Testing the primary hypothesis in this study.

We have estimated the sample size of the prospective cohort based on the primary hypothesis that individuals experiencing the intervention of Phase III will have higher levels of effective use of SARS-CoV-2 testing than their testing at baseline. The McNemar test, together with the odds ratio (OR) of COVID-19 testing for post-intervention versus baseline, will be used to assess the intervention effect. Preliminary data yielded a discordance of 19% between baseline and follow-up measurements. The ORs were 3.4, 2.3, and 2.3 for Harris, Cameron, and NETX, respectively. The OR for the pooled data was 2.55. We use an OR of 2.5 and a discordance of 19%, which represents an 8% difference in the proportion of testing at follow-up compared to baseline, to size the prospective cohort. For a one-sided test at the significance level of 2.5%, a **sample size of 237 is needed to provide 80% power** for confirming the intervention effect. To allow for a **45% loss to follow-up**, 431 participants need to be enrolled at baseline. The table below provides the size options for a one-sided McNemar test of alpha 2.5% and power 80%.

Proportion of discordance	Odds ratio (OR)	Difference in proportion of testing pertaining to OR	Required sample size	Enrollment allows for a 35% loss to follow-up	Enrollment allows for a 45% loss to follow-up
0.19	2	6%	393	605	715
0.19	2.5	8%	237	365	431
0.19	3	9.5%	177	273	322
0.3	1.5	6%	681	1048	1239
0.3	1.727	8%	387	596	704
0.3	2	10%	249	384	453
0.3	2.75	14%	128	197	233

**Statistical Analysis - MC-NET-JITAI.** We will analyze the secondary outcome measures using the McNemar test, conditional logistic regression model, generalized linear mixed model (GLMM). The enrolled individuals completing the follow-up survey constitute the analysis set. In GLMM, we will specify proper random effects to account for hierarchical nesting structure. Secondary analyses will examine the relation between knowledge, attitudes, and intentions on testing and vaccination decisions and we will use the same multilevel GLMM models.

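### Part B of the baseline survey has no completion window and need not precede the intervention, so any analysed item placed there may be measured after exposure and still be labelled baseline

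*Combined protocol and SAP*

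**What the plan says.** The Recruitment section splits the baseline survey in two. Of the first part it says: "The baseline survey includes part A, which is completed at the actual time of enrollment". If there is no time at the visit, part A is done at a return visit within 7 days or virtually. Of the second part it says: "Part B of the survey will also be sent to the participant electronically so that they can complete those items at their convenience". It gives no last date for part B and no rule for answers that arrive late.

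What follows enrolment is tied to part A only. On materials: "After part A of the survey is completed, study personnel will provide participants with a COVID-19 resource flier". On payment: "Upon completion of the baseline survey part A, the participant will receive the first incentive card". Staff also take contact details at that point so that they can "follow up throughout the 8 weeks period with intervention related messages or answer participant questions".

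The Intervention Arms text under Project Materials describes texts at a rate of "up to three messages each week, providing updates on COVID-19 testing and vaccination", together with four antigen tests and updated testing and vaccination information from the community health worker.

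The Statistics section screens demographics and prior rapid-test use at baseline as model covariates. The paragraph on MC-NET-JITAI analyses adds: "Secondary analyses will examine the relation between knowledge, attitudes, and intentions on testing and vaccination decisions".

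**The concern.** A baseline value should be taken before the intervention can act on it. For part B the plan states a rule that does not secure this: the participant chooses when to answer, and the intervention does not wait.

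Suppose an item on intention, self-efficacy, perceived risk or recent test use sits in part B and is answered some weeks in. Its recorded baseline may then already reflect the flier, the messages or the kits. Two things follow for that item. Any pre-post change would usually be understated. As a covariate or determinant it would be partly a consequence of the intervention, so the time order that the model assumes is lost. Without a pre-specified rule, the analyst would also have to decide what to do with late answers after seeing the data.

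**Working it through.** **1. Timing rules side by side.**

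| Element | Earliest | Latest | Source |
|---|---|---|---|
| Part A | enrolment | return visit within 7 days, or virtual option | Recruitment |
| Part B | when sent | not stated | Recruitment |
| Follow-up survey | 5 weeks after initial visit (target 8) | about 4 months | Recruitment |

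Part B is the only survey element without a limit. Nothing says that it must be done before the follow-up survey.

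**2. What can come before part B.** The flier does not wait for part B; this is documented. Messages run through the 8 weeks, but the date of the first one is not given. The day the kits are handed over is not given either. Two clocks suggest that the intervention starts at about the first visit: follow-up is counted 8 weeks from the initial home visit (Recruitment) and two months from the initial intervention (Intervention Arms). That is an inference. If texts did start at once, a participant could have had up to 3 × 2 = 6 of a maximum 3 × 8 = 24 messages by the end of week 2, or 25%.

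**3. Which analyses could be touched.** The declared outcomes are antigen testing, vaccination and mitigation behaviours. The survey table lists these alongside intention, self-efficacy and perceived risk, but assigns nothing to part A or part B. The exposed uses are therefore conditional: any outcome, covariate or determinant item that is in part B.

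**4. The plan's own figure.** With discordance 0.19, OR 2.5 and one-sided alpha 0.025, the share of discordant pairs in favour is 2.5/3.5 = 0.714 and the difference is 0.19 × 1.5/3.5 = 0.0814. The exact McNemar test, with the number of discordant pairs binomial (N, 0.19), first reaches 80% power at N = 237 (80.01%). Then 237/0.55 = 430.9, so 431 enrolled. Both figures reproduce, and the part B rule does not alter them.

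**5. Size for a part B item (assumptions, not plan figures).** Let r be the share answering late and g the fraction of the full effect already present in their answers. Then measured change = (1 − r·g) × true change.
- g = 1: r = 20% loses 20%; r = 50% loses half. This is the upper bound for an effect that builds up over time.
- g = 0.25 (effect proportional to 6 of 24 messages): r = 20% loses 0.20 × 0.25 = 5%; r = 50% loses 12.5%.

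The documents supply neither r nor g.

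**6. Direction for the primary outcome, if its item were in part B.** The eligibility criteria exclude anyone tested in the past 30 days. A late answer to a last-30-days item can therefore only add tests done after enrolment. That turns an untested-then-tested pair into a concordant one, or an untested-untested pair into one that counts against the intervention. Both shrink the difference.

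For scale, suppose the testing item is in part B, a fraction f of baseline answers already equals follow-up status, and the OR among the remaining discordant pairs stays at 2.5:

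| f | Discordance 0.19(1 − f) | Exact power at N = 237 | N for 80% power |
|---|---|---|---|
| 0 | 0.190 | 80.0% | 237 |
| 10% | 0.171 | 75.0% | 264 |
| 20% | 0.152 | 68.8% | 297 |
| 50% | 0.095 | 45.4% | 475 |

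If the testing item is in part A, this table does not apply.

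**The case against.** The strongest reply is that the harm rests on content not shown. The survey is listed as an attachment and is not in the text available, so the split of items cannot be called missing from the plan. If part B holds demographics or pre-enrolment history, late answers do little harm. This stands, and it is why the point is conditional.

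Second, the Subject Duration entry in the opening table gives the order as enrolment, baseline survey, then texts. The Data Collection section also has weekly checks for incomplete data, and staff who can close surveys and send reminders. These may shorten delays. They set no cutoff, however, and chasing a missing part B can itself produce a late one.

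Third, knowledge, attitudes and intentions are not declared outcomes. The planned analysis of them is one of association, and it is not said to use baseline values or change scores. This stands too: no planned change analysis of those constructs is shown to shrink. The loss of time order remains possible wherever a baseline value is used.

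A reader might infer that the primary McNemar result is contaminated, that power falls to the values tabulated above, or that each late answer costs a full unit of effect. The documents support none of these. Nothing places the testing item in part B, no late share is given, and a full effect in every late answer is an assumption. Nor do they show that part B is in fact answered after texts begin; they only permit it. Payment after part A alone bears mainly on whether part B is completed at all.

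**Conclusion.** The gap in the rule is real: part B carries the baseline label, has no completion window and is not required before intervention contact. Any analysed item placed there may be measured after exposure.

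Its effect is unquantified. It depends on which items are in part B, when the first text is sent and how many participants answer late. For an effect that builds up, the share of change lost on a part B item lies between zero and the late share r. For the primary outcome no effect is shown, and if the item were in part B the bias would work against finding a benefit, so this is not a route to a false positive there. The sample size is not in dispute. This is a cheap improvement to the design; it does not invalidate the planned analysis. If every analysed item is already in part A, one sentence saying so closes the point.

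**What to change.** State which constructs are in part A and which in part B. Then do one of the following:
- keep every outcome item and every analysed baseline covariate or determinant in part A; or
- require part B to be completed before the first intervention text. This is the weaker option, because the flier still follows part A.

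In either case, record the part B completion date in REDCap, flag answers given after the first message, and pre-specify that analyses using part B baseline items are run with and without the flagged answers. A sensitivity analysis is preferable to setting late answers to missing automatically, since the study already allows for 45% loss to follow-up. The data management text describes an audit trail, so flagging should be feasible for participants already enrolled.

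The cost is a slightly longer part A, in a visit that may already take up to 1 hour, or a short delay before the first text. Some part B values will also drop out of the sensitivity analysis. Planned enrolment does not change.
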